### **15.2. Publications by Investigators**

Pfizer supports the exercise of academic freedom and has no objection to publication by the principal investigator (PI) of the results of the study based on information collected or generated by the PI, whether or not the results are favorable to the Pfizer product. However, to ensure against inadvertent disclosure of confidential information or unprotected inventions, the investigator will provide Pfizer an opportunity to review any proposed publication or other type of disclosure of the results of the study (collectively, “publication”) before it is submitted or otherwise disclosed.

The investigator will provide any publication to Pfizer at least 30 days before it is submitted for publication or otherwise disclosed. If any patent action is required to protect intellectual property rights, the investigator agrees to delay the disclosure for a period not to exceed an additional 60 days.

The investigator will, on request, remove any previously undisclosed confidential information before disclosure, except for any study- or Pfizer product-related information necessary to the appropriate scientific presentation or understanding of the study results.

If the study is part of a multicenter study, the investigator agrees that the first publication is to be a joint publication covering all investigator sites, and that any subsequent publications by the PI will reference that primary publication. However, if a joint manuscript has not been submitted for publication within 12 months of completion or termination of the study at all participating sites, the investigator is free to publish separately, subject to the other requirements of this section.

For all publications relating to the study, the institution will comply with recognized ethical standards concerning publications and authorship, including Section II - "Ethical Considerations in the Conduct and Reporting of Research" of the Uniform Requirements for Manuscripts Submitted to Biomedical Journals, <http://www.icmje.org/index.html#authorship>, established by the International Committee of Medical Journal Editors.

Publication of study results is also provided for in the CSA between Pfizer and the institution. In this section entitled Publications by Investigators, the defined terms shall have the meanings given to them in the CSA.

If there is any conflict between the CSA and any attachments to it, the terms of the CSA control. If there is any conflict between this protocol and the CSA, this protocol will control as to any issue regarding treatment of study subjects, and the CSA will control as to all other issues.

## Appendix 1. Abbreviations

This following is a list of abbreviations that may be used in the protocol.

Abbreviation	Term
AD	atopic dermatitis
ADSI	atopic dermatitis severity index
AE	adverse event
ALT	alanine aminotransferase
AST	aspartate aminotransferase
AUC	area under the concentration time curve
BBS	biospecimen banking system
BP	blood pressure
BID	twice a day
BSA	body surface area
cAMP	cyclic adenosine monophosphate
CI	confidence interval
CK	creatin kinase
C max	maximum plasma concentration
CRF	case report form
CRU	Clinical Research Unit
CSA	clinical study agreement
CSF	cerebrospinal fluid
CSR	clinical study report
CT	Clinical Trial
CTA	clinical trial application
CTCAE	Common Terminology Criteria for Adverse Events
DCs	dendritic cells
DDI	drug drug interaction
DILI	drug-induced liver injury
DMC	data monitoring committee
DNA	deoxyribonucleic acid
DU	dispensable unit
CCI	
EC	ethics committee
EC 50	half maximal effective concentration
ECG	Electrocardiogram
E-DMC	external data monitoring committee
EDP	exposure during pregnancy
EU	European Union
EudraCT	European Clinical Trials Database
FDA	Food and Drug Administration
FLG	filaggrin
GCP	Good Clinical Practice
GGT	Gamma-glutamyl transferase

Abbreviation	Term
GSVA	Gene Set Variation Analysis
H&E	hematoxylin and eosin
hARP	human acidic ribosomal protein gene
HIV	human immunodeficiency virus
HRQL	health-related quality of life
HRQoL	health-related quality of life
IB	investigator's brochure
ICH	International Conference on Harmonisation
ID	identification
IGA	Investigator's global assessment
IgE	immunoglobulin E
IHC	immunohistochemistry
IND	investigational new drug application
INR	international normalized ratio
IP	investigational product
IRB	institutional review board
IRC	internal review committee
IRT	interactive response technology
ISGA	investigator static global assessment
IUD	intrauterine device
IWR	interactive web response
K 2 EDTA	dipotassium ethylenediaminetetraacetic acid
LFT	liver function test
LMW	low molecular weight
LOR	loricrin
LSLV	last subject last visit
MedDRA	Medical Dictionary for Regulatory Activities
MnB	meningitidis serogroup B
N/A	not applicable
NRS	numeric rating scale
NSAID	nonsteroidal anti-inflammatory drug
PCD	primary completion date
PCR	polymerase chain reaction
PD	Pharmacodynamics(s)
PDE-4	phosphodiesterase-4
PE	physical examination
PFS	prefilled syringe
PGx	Pharmacogenomics(s)
PI	principal investigator
PK	pharmacokinetic
PKA	protein kinase A
PMA	phorbol 12-myristate 13-acetate
PT	prothrombin time

Abbreviation	Term
QD	once a day
RNA	ribonucleic acid
RT	reverse transcriptase
SAE	serious adverse event
SAP	statistical analysis plan
SC	subcutaneous
SD	standard deviation
SOC	system organ class
SOP	standard operating procedure
SRSD	single reference safety document
SUSAR	suspected unexpected serious adverse reaction
TBili	total bilirubin
TEAE	treatment emergent adverse events
CCI	
TLDA	Taqman Low Density Array
TQT	thorough QT
TSLP	thymic stromal lymphopoietin
TSS	total sign score
ULN	upper limit of normal
US	United States
UV	ultraviolet

## **Appendix 2. Diagnostic Criteria for Atopic Dermatitis**

Per Inclusion Criterion 2, a subject is to have a clinical diagnosis of atopic dermatitis according to the criteria of Hanifin and Rajka or at least 6 months prior to Screening visit and that has been clinically stable for  $\geq 1$  month.

**Table 4: Hanifin and Rajka's Diagnostic Criteria for Atopic Dermatitis**

---

### **Major Criteria (must have at least three)**

Pruritus

Typical morphology and distribution:

Adults: flexural lichenification or linearity

Children and infants: involvement of facial and extensor surfaces

Chronic or relapsing dermatitis

Personal or family history of atopy

---

### **Minor Criteria (must have at least three)**

Xerosis

Icthyosis/keratosis pilaris/palmer hyperlinearity

Immediate (type 1) skin test reactivity

Elevated serum immunoglobulin E (IgE)

Early age at onset

Tendency to skin infections (Staphylococcus aureus, herpes simplex)/impaired cellular immunity

Hand/foot dermatitis

Nipple eczema

Conjunctivitis

Dennie-Morgan fold

Keratoconus

Anterior subcapsular cataracts

Orbital darkening

Facial pallor/erythema

Pityriasis alba

Anterior neck folds

Itch when sweating

Intolerance to wool and lipid solvents

Perifollicular accentuation

Food intolerance

Course influenced by environmental/emotional factors

White demographic/delayed blanch

---

1. VERSION HISTORY

This Statistical Analysis Plan (SAP) for study C3291001¹ is based on the protocol dated 02May2017.

Table 1. Summary of Major Changes in SAP Amendments

SAP Version	Change	Rationale
1	Not Applicable	Not Applicable
2	
Additional Day 15 visit window for ISGA (global), CCI [REDACTED] and pruritus NRS (global) was added
 
AR(1) variance-covariance matrix was added to Section 5.2.2 for mixed model.
 
Summary of pruritus NRS change from Day 15 to Day 43 was updated as change from Day 15 to Day 16 through Day 43.
 
TEAE definition was updated
 
CCI [REDACTED]
 
Line plots for mean change (\pm SE) from baseline up to Day 15, and mean change (\pm SE) from Day15 to Day 16 through Day 43 in pruritus NRS were added.
	
No Day 8 assessments for these endpoints
 
In case there is convergence issue for unstructured variance-covariance matrix.
 
Pruritus NRS was collected daily.
 
Per Pfizer Standard

2. INTRODUCTION

Crisaborole, also referred to as PF-06930164 and AN2728, is a low molecular weight benzoxaborole anti-inflammatory phosphodiesterase-4 (PDE-4) inhibitor. The safety and efficacy of crisaborole has been demonstrated in two phase 3 studies (AN2728-AD-301 and AN2728-AD-302) and one long term open-label study (AN2728-AD-303). The 2% dose strength of crisaborole ointment is approved in the US for the treatment of mild-moderate atopic dermatitis (AD) for subjects ≥ 2 years.

The specific mechanism(s) by which crisaborole exerts its therapeutic action is not well defined. In this study, skin biopsies will be collected to characterize the mechanism of action, by evaluation of efficacy and changes in key skin biomarkers, of crisaborole ointment 2% over vehicle, applied twice a day in adult subjects with AD with maximum treatable BSA of 10%. The skin biopsy samples will be analyzed using immunohistochemistry (IHC) and gene expression, which will be done using TLDA PCR for 48 genes including housekeeping genes as well as single gene PCR for a few genes that are below detection level on TLDA.

This SAP provides the detailed methodology for summary and statistical analyses of the data collected in study C3291001.¹ This document may modify the plans outlined in the protocol; however, any major modifications of the primary endpoint definition or its analysis will also be reflected in a protocol amendment.

2.1. Study Objectives

2.1.1. Primary Objectives

- To evaluate the efficacy of crisaborole ointment 2% vs vehicle in subjects with mild to moderate AD.*
- To evaluate change in key skin biomarkers of AD in target lesions treated with crisaborole ointment 2% or vehicle.*

2.1.2. Secondary Objectives

- To evaluate change in other skin biomarkers of atopic dermatitis in target lesions treated with crisaborole ointment 2% or vehicle.*
- To evaluate normalization of biomarker and gene expression levels in lesional skin treated with crisaborole ointment 2% or vehicle.*
- To evaluate changes in AD clinical sign and symptom severity in target lesions treated with crisaborole ointment 2% or vehicle.*
- To assess the safety and local tolerability of crisaborole ointment 2% in subjects with mild to moderate AD.*

CCI

- CCI [REDACTED]

2.2. Study Design

This is a Phase 2a randomized, double-blind, vehicle-controlled study to characterize the mechanism of action, by evaluation of efficacy and changes in key skin biomarkers, of crisaborole ointment 2% in subjects with mild to moderate atopic dermatitis. After completing screening activities, including meeting eligibility criteria, approximately 40 subjects will be treated. In the double-blind treatment period, each subject will be randomly assigned to be treated with crisaborole ointment 2% for one target lesion. The other target lesion will receive vehicle.

The double-blind treatment period will last from Baseline/Day 1 to Day 15 skin biopsy collection and will include twice daily visits to the site for IP application and study assessments, where applicable. The open-label treatment period will start from the Day 15 skin biopsy collection and last until Day 43 (end of treatment/early termination); during this time, subjects will be able to treat all AD skin areas (except scalp), at home, with crisaborole ointment 2%.

Scheduled (outpatient) study visits for all subjects will occur at Screening (up to 30 days prior to Day 1/Baseline), Days 1 to 14 (twice daily), Day 15, and Day 43 (end of treatment/early termination). On Day 71 (end of study), a follow-up telephone call will be made by site staff to assess for AEs that may have occurred since the last visit.

3. ENDPOINTS AND BASELINE VARIABLES: DEFINITIONS AND CONVENTIONS

3.1. Primary Endpoint(s)

- *Change from baseline in TSS in target lesions treated with crisaborole ointment 2% or vehicle on Day 15.*
- *Change from baseline in key skin biomarkers of AD (S100A12, CCL17, CCL18, CCL22, K16, elafin/PI3 and IL-13 expression level) in target lesions treated with crisaborole ointment 2% or vehicle at Day 15.*

3.2. Secondary Endpoint(s)

- *Change from baseline in other skin biomarkers in target lesions treated with crisaborole ointment 2% or vehicle at Day 15.*
- *Biomarker and gene expression level in lesional skin treated with crisaborole ointment 2% or vehicle at Day 15 and levels in non-lesional skin at Baseline.*
- *Change from baseline in lesion severity as measured by TSS, ISGA, and Pruritus Numerical Rating Scale at each visit up to Day 15.*
- *The incidence of treatment emergent AEs and SAEs.*

CCI [REDACTED]

- █ [REDACTED]
- █ [REDACTED]
- █ [REDACTED]
- █ [REDACTED]
- █ [REDACTED]
- █ [REDACTED]

3.4. Baseline Variables

Demographic and baseline characteristics include:

- Age (in years);
- Sex;
- Race;
- Ethnicity;
- Height (in cms);
- Weight (in kg);
- Body Mass Index;
- Duration of disease (in years);
- ISGA (global and target lesions);
- CCI [REDACTED]
- CCI [REDACTED]
- TSS (target lesions);
- CCI [REDACTED]
- Pruritus numerical scale (global and target lesions).

3.5. Safety Endpoints

3.5.1. Adverse Events

- *All adverse events (AEs), including serious adverse events (SAEs).*

An AE is considered treatment emergent relative to a given treatment if:

- The event occurs for the first time during the effective duration of treatment and was not seen prior to the start of treatment (eg, during the screening period), or
- The event was seen prior to the start of treatment but increased in severity during treatment, or
- The event was seen and was resolved prior to the start of treatment but reported again during treatment.

3.5.2. Laboratory Data

- Clinically significant abnormal laboratory parameters.
- Clinical laboratory values and change from screening at Day 43/Early Termination.

4. ANALYSIS SETS

4.1. Full Analysis Set

The full analysis set (FAS) includes all subjects who are randomized and receive at least one dose of investigational product.

4.2. Per Protocol Analysis Set

The Per Protocol Analysis Set (PPAS) will be a subset of subjects from FAS. PPAS *includes any subject randomized and receiving ≥ 1 dose of investigational product, with both Day 1 and Day 15 biopsies done, and without protocol violations that were thought to impact the biomarker expression during the vehicle controlled period. All protocol deviations will be reviewed and assessed by the study team prior to database release. In general, all data will be summarized using descriptive statistics. No imputation will be made for missing data.*

4.3. Safety Analysis Set

The Safety Analysis Set *will include any subject receiving ≥ 1 dose of investigational product.*

4.4. Other Analysis Sets

N/A.

5. GENERAL METHODOLOGY AND CONVENTIONS

5.1. Hypotheses and Decision Rules

One of the primary analyses will be a superiority test to demonstrate crisaborole ointment 2% is more efficacious than vehicle in the target lesion in subjects with mild to moderate AD as measured by the change from baseline in target lesion severity score (TSS) between crisaborole treated lesion and vehicle treated lesion. The null hypothesis is that there is no difference between crisaborole ointment 2% and vehicle, and the alternative hypothesis is that crisaborole ointment 2% is superior to vehicle as measured by change from baseline in TSS at Day 15. The difference between crisaborole and vehicle in TSS change from baseline at Day 15 is significant if $p\text{-value} < 0.05$.

Another primary analysis is for the change in the key skin biomarkers S100A12, CCL17, CCL18, CCL22, elafin/PI3, K16, or IL-13 in the target lesion treated with crisaborole 2% ointment or vehicle. The null hypothesis is that there is no difference between crisaborole ointment 2% and vehicle in the change from baseline to Day 15 in these biomarkers, and the alternative hypothesis is that there is a difference between crisaborole ointment 2% and vehicle in the expression level of biomarkers. Mixed effect model will be used and p-values will be adjusted by Benjamini-Hochberg procedure.

5.2. General Methods

In general, number and percent will be presented for categorical variables. Number, mean, standard deviation, minimum, 1st, 2nd and 3rd quartiles and maximum will be presented for continuous variables.

5.2.1. Analyses for Binary Data

Lesion ISGA response of clear or almost clear and at least a 2 grade improvement from Baseline to Day 8 and Day 15 will be descriptively summarized using number, percentage and 95% confidence interval (CI) of percentage, and compared using McNemar's test for the comparison of crisaborole vs vehicle at each time point.

CCI

5.2.2. Analyses for Continuous Efficacy Data

For the lesion TSS, the linear mixed model will be used to model the intra-subject change from baseline in TSS between the crisaborole ointment 2% treated lesion and vehicle treated lesion. The model includes the fixed effect of visit as factor, and an unstructured variance and covariance matrix will be used to model the dependence among the same subjects across different visits up to Day 15. If there is convergence issue for unstructured variance-covariance matrix, first order autoregressive (AR(1)) variance-covariance matrix will be used. The least square (LS) mean of difference and the associated 95% CI will be presented. CCI

Continuous secondary endpoints in the double blind period:

- Change from baseline in lesion ISGA up to day 15;

CCI

- Change from baseline in lesion pruritus numerical rating scale up to Day 15.

will be analyzed using similar methods as lesion TSS.

CCI

will be descriptively summarized using number, mean, standard deviation, minimum, 1st, 2nd and 3rd quartiles and maximum.

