### **9.1. Sample Size Determination**

The sample size of this study is based on the objective to demonstrate crisaborole ointment 2% is more efficacious than vehicle in the target lesion in subjects with mild to moderate AD as measured by the change from baseline in target lesion severity score (TSS) between crisaborole treated lesion and vehicle treated lesion.

Approximately 40 subjects will be enrolled in the study to ensure approximately 30 subjects who will have skin biopsy done at Day 15 during the double-blind treatment period to have the precision described below (considering the non-compliance during the double-blind treatment period is ~20%).

A sample size of 40 will have 90% power to establish the superiority of crisaborole to vehicle as measured by the change from baseline in TSS between crisaborole treated lesion and vehicle treated lesion at Day 15 using paired t-test at 0.05 (one-sided) significance level, assuming the difference is 1.4 and standard deviation 3. With sample size of 30, the power becomes 80%.

A sample size of 30 also provides the following precision to estimate the change in the key skin biomarkers S100A12, CCL17, CCL18, CCL22, elafin/PI3, K16, or IL-13 in the target lesion treated with crisaborole 2% ointment or vehicle. The expression level of biomarkers at Baseline or Day 15 will be expressed as log2 transformed fold change (FCH) relative to house-keeping gene human acidic ribosomal protein gene (hARP), ie, the ratio between expression level of each biomarker and the expression level of hARP for each RT PCR sample. The margin of error for the estimates, ie, the half width of the 95% confidence intervals (CIs) for the change from baseline in FCH, is less than 1.1 under the assumption that the maximal standard deviations for the change in FCH is 3 based on unpublished data.

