6.2. Secondary Endpoint(s)

6.2.1. Change in The Lesion TSS From Baseline to Day 8

Day 8 is a time point in the mixed model for the primary analysis for lesion TSS change from baseline at Day 15. The analysis for lesion TSS change at Day 8 is from the same model, and data reporting is same as for Day 15. See [Section 6.1.1](#).

6.2.2. Changes in Key Skin Biomarkers From Baseline to Day 8

Day 8 is a time point in the mixed model for the primary analysis for biomarkers change from baseline at Day 15. The analysis for biomarkers change at Day 8 is from the same model, and data reporting is same as for Day 15. See [Section 6.1.2](#).

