6.2.4. Change From Baseline to Day 8 and Day 15 in ISGA

6.2.4.1. Primary Analysis

- Analysis time points: Day 8 and Day 15.
- Analysis population: FAS.
- Analysis methodology: the intra-subject difference of change from baseline in lesion ISGA between crisaborole and vehicle will be analyzed using the model specified in [Section 5.2.2](#).
- Imputation for missing values: observed data will be included in the model, the missing values will be handled in the model, where the values are assumed to be missing at random.

Reporting results:

- Raw data: The sample size, number and percentage for each category at baseline and post-baseline visits will be presented for each treatment.
- Change from baseline: The sample size, mean, standard deviation, median, Q1, Q3, minimum and maximum will be presented for each treatment. The LS means of difference and the corresponding standard error, 95% CI, p-value will be presented.
- Shift table: number and percentage from each category at baseline to each category at Day 8 and Day 15 will be presented.

6.2.5. Change From Baseline To Visits Up To Day 15 In Pruritus Numerical Scale

- Analysis time points: Day 2 to Day 15
- Analysis population: FAS
- Analysis methodology: the intra-subject difference of change from baseline in lesion pruritus between crisaborole and vehicle will be analyzed using the model specified in [Section 5.2.2](#).
- Imputation for missing values: observed data will be included in the model, the missing values will be handled in the model, where the values are assumed to be missing at random.

[figure not shown]
Reporting results:

- Raw data: The sample size, mean, standard deviation, median, Q1, Q3, minimum and maximum at baseline and post-baseline visits will be presented for each treatment.

[figure not shown]
- Change from baseline: The sample size, mean, standard deviation, median, Q1, Q3, minimum and maximum will be presented for each treatment. The LS means of difference and the corresponding standard error, 95% CI, p-value will be presented.
- Plot: Line plot will be provided for mean change (\pm SE) from baseline.

CCI

CCI

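### The only covariance fallback, plain AR(1), assumes equal variance at every visit; if it is used for daily lesion pruritus, the Day 15 and early-visit standard errors could be wrong in opposite directions.

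*SAP*

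**What the plan says.** SAP 5.2.2 models the within-subject crisaborole-minus-vehicle difference in change from baseline, with visit as a factor. The first-choice covariance is unstructured: "an unstructured variance and covariance matrix will be used to model the dependence among the same subjects across different visits up to Day 15". One alternative is given: "If there is convergence issue for unstructured variance-covariance matrix, first order autoregressive (AR(1)) variance-covariance matrix will be used". No heterogeneous version, intermediate structure or robust standard error is named.

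The section then lists other continuous endpoints, lesion pruritus among them, that "will be analyzed using similar methods as lesion TSS". SAP 6.2.5 sets the pruritus visits: "Analysis time points: Day 2 to Day 15". Its reporting list includes inference: "The LS means of difference and the corresponding standard error, 95% CI, p-value will be presented". Unlike SAP 6.1.1.1 for TSS, SAP 6.2.5 states no decision rule.

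For TSS the model has two post-baseline visits, as SAP 6.2.1 shows: "Day 8 is a time point in the mixed model for the primary analysis for lesion TSS change from baseline at Day 15".

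**The concern.** Plain AR(1) has two parameters: one variance shared by all visits and one correlation. The standard error at each visit is then driven by the pooled variance, not by that visit's own variance.

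A change from baseline is a natural candidate for unequal variance. Day 2 is one day from baseline and Day 15 is fourteen. If daily scores are correlated and the correlation fades with time, the change varies more at later visits, and differing treatment response between subjects would add to that.

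If the fallback is used and the variance does rise, the Day 15 confidence interval is too narrow and its p-value too small, while the early-visit intervals are too wide. What is at stake is the accuracy of reported intervals and p-values for a secondary endpoint.

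**Working it through.** **The plan's nearest figure.** Protocol 9.1 gives power for TSS, "using paired t-test at 0.05 (one-sided) significance level, assuming the difference is 1.4 and standard deviation 3". A noncentral-t calculation returns 89.5% at 40 subjects and 80.3% at 30, matching the stated 90% and 80%. That SD is for TSS at Day 15. Neither document gives an SD for pruritus, or an SD by visit for any endpoint.

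**Parameter counts.** Pruritus has 14 visits (Day 2 to Day 15): unstructured 14 × 15 / 2 = 105, AR(1) 2, heterogeneous AR(1) 14 + 1 = 15. TSS has 2 visits: unstructured 2 × 3 / 2 = 3, AR(1) 2.

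**Effect on the standard error.** With complete data and visit as a saturated factor, the Day 15 LS mean is the Day 15 sample mean under any covariance structure. Therefore

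model SE / true SE at Day 15 = √(pooled AR(1) variance / true Day 15 variance).

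Assume the SD moves linearly from 1 on Day 2 to r on Day 15. As a close approximation, take the pooled variance as the average over the 14 visits:

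mean variance = r + (r − 1)² × 819 / (14 × 169) = r + 0.346 (r − 1)²,

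where 819 is the sum of k² for k = 0 to 13 and 169 = 13². The two-sided type I error is approximately 2Φ(−1.96 × Day 15 ratio).

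| r (assumed) | Mean variance | Day 15 SE ratio | Day 2 SE ratio | Type I error, Day 15 |
|---|---|---|---|---|
| 0.67 | 0.708 | 1.26 | 0.84 | 1.4% |
| 1 | 1.000 | 1.00 | 1.00 | 5.0% |
| 1.25 | 1.272 | 0.90 | 1.13 | 7.7% |
| 1.5 | 1.587 | 0.84 | 1.26 | 10.0% |
| 1.75 | 1.945 | 0.80 | 1.39 | 11.8% |
| 2 | 2.346 | 0.77 | 1.53 | 13.3% |
| 3 | 4.385 | 0.70 | 2.09 | 17.1% |

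The exact large-sample AR(1) fit, minimising log|V| + tr(V⁻¹Σ) under several true correlation patterns, gives nearly the same Day 15 ratios: 1.26, 1.00, 0.90, 0.84, 0.80, 0.77–0.78 and 0.70–0.72. At r = 2 it puts the Day 2 standard error about 54% too large.

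**Finite-sample check.** 1,000 simulated trials per case, 40 subjects, 8 with monotone dropout (20%), AR(1) fitted by REML:

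- Constant SD: Day 15 ratio 0.98–1.02, type I error 4–5%.
- 1.5-fold: ratio 0.83–0.86, type I error about 9%.
- 2-fold: ratio 0.74–0.77, type I error 12–14%.

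**Baseline subtraction alone.** Suppose the daily between-lesion difference is stationary with variance σ² and correlation φ^h at lag h. The change at lag h then has variance 2σ²(1 − φ^h), with h = 1 on Day 2 and h = 14 on Day 15.

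- φ = 0.95: Day 2 variance 0.10σ², Day 15 variance 1.02σ², average 0.61σ². The averaging approximation gives √(0.61 / 1.02) = 0.77; the exact AR(1) limit is 0.76.
- φ = 0.7: Day 15 variance 1.99σ², average 1.67σ². The approximation gives 0.92; the exact limit is 0.89.
- With 20% of σ² as measurement noise, the exact limits run from 0.92 (φ = 0.7) to 0.85 (φ = 0.95).

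Across daily correlations of 0.7–0.95, with or without that noise, the Day 15 standard error is 8–24% too small.

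**The case against.** The strongest reply is that the fallback may never be used. A count of 105 parameters does not show non-convergence. With complete data and visit as the only factor, the unstructured estimate is the sample covariance matrix, which exists with 30–40 subjects and 14 visits. In 120 simulated data sets (36 subjects, integer-rounded scores, 5% intermittent missingness plus 4 dropouts), an EM fit of the unstructured model reached a positive-definite matrix in 118. Other optimisers may behave differently, but failure should not be presumed common. This stands: the defect is conditional.

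The direction and size are also assumed. Baseline subtraction makes rising variance plausible, but no figure in the documents shows it, and a falling SD would make the Day 15 test conservative. This stands too.

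The visit-window table in SAP 9.1 groups Day 2 to Day 11 as Day 8. Applied to lesion pruritus, it would leave two visits. SAP 6.2.5 nevertheless lists Day 2 to Day 15, and the version history in SAP Section 1 notes that pruritus was collected daily, so 14 visits is the better reading.

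A reader might go further in three ways that the documents do not support:

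- That the primary TSS result is at risk. Its model has two visits and three unstructured parameters, so the fallback is unlikely to be needed.
- That SAP version 2 added AR(1) because of pruritus. The version history mentions only a possible convergence issue and names no endpoint.
- That Day 15 is the key pruritus time point. SAP 3.2 defines the endpoint at each visit up to Day 15.

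None of this is an argument for equal variances as the only alternative.

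**Conclusion.** The point holds as a conditional weakness. If the unstructured pruritus model fails to converge, the named fallback gives a wrong standard error, interval and p-value at any visit whose variance differs from the pooled value. Under linear SD growth the Day 15 error runs from none (constant SD) to about 30% too small (3-fold), and it is about 26% too large if the SD falls by a third.

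It is tempting to quote a 20–25% understatement as the expected result. That needs the SD to grow roughly 1.75- to 2.2-fold, which nothing in the documents establishes. Nor is the error anti-conservative throughout: when Day 15 is understated, the early visits are overstated.

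With a secondary endpoint, no decision rule and a fallback that may not be used, this is a low-priority improvement.

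**What to change.** In SAP 5.2.2, replace the plain AR(1) sentence with a pre-specified order:

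1. Unstructured.
2. If that does not converge, a structure with visit-specific variances, for example heterogeneous AR(1).
3. If that also fails, a simple structure with empirical (sandwich) standard errors and a small-sample correction.

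The SAP should also require the report to state which structure was used for each endpoint.

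The cost is a sentence or two. Statistically, heterogeneous AR(1) estimates 15 covariance parameters instead of 2, so the variance estimates are slightly less precise if the variance really is constant. Heterogeneous AR(1) is one reasonable choice among several; what matters is that the variance may differ by visit and that the list ends in a step that can be fitted.
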